14.4 Audit and Inspection

There may be a possibility that the Quality Assurance Department of the sponsor or the Regulatory Authorities may audit or inspect the site to verify compliance to protocol, procedures and applicable regulations.

The investigator will permit to be audited/inspected by sponsor personnel and/or Regulatory Authorities during and/or after the study has been completed.

14.5 Adherence to Protocol

Protocol deviations will be reported to the sponsor who will assess their significance (Major and Minor) with regards to the impact on the rights, safety, and well-being of human subjects, and to the impact on quality and data integrity. All deviations will be reported and discussed in the study report.

In case of a protocol amendment, before the suggested modifications will be implemented, the sponsor will notify the new version of the protocol to the relevant IEC and authorities, specifying whether the modifications are substantial/not-substantial and, if applicable, will put the study on hold until the re-approval will be obtained, if applicable.

14.6 Data Handling and Retention

The sponsor and the investigator assume the responsibility to assure that the clinical data will be collected according to the CIP requirements (no additional data will be collected), local laws and obligations and the World Medical Association Declaration of Helsinki. The clinical data obtained as a result of this study is considered confidential between the site and the sponsor: disclosures to third part are prohibited or, if necessary for example to perform statistical analysis with contracted vendors, will be protected by non-disclosure agreements.

Before the Site Initiation Visit, the sponsor will provide an eCRF system (Castor) that is validated according to applicable laws and regulations, including 21 CFR Part 11, EU Annex 11, General Data Protection Regulation (GDPR), HIPAA (US), ISO 9001 and ISO 27001. The Sponsor will provide training to the Investigators/CRA about the data entry procedures and queries solving. The clinical data entered in the eCRF must come from the source data, that is all information in original (or certified copies) reported in source documents (for example: patients' clinical records, records of clinical findings, investigator's observations/assessment).

The investigator assumes the responsibility to assure that the last data will be entered within 1 month after the last patient last visit (including all queries resolution).

The investigator will have to keep all study related documentation for the longest possible duration, but at least for 15 years after the completion or premature termination of the study. No data should be destroyed without agreement with the sponsor. The Sponsor will maintain all documentation pertaining to the study for the lifetime of the product.

Sponsor and investigators shall take measures to prevent accidental or premature destruction of these documents and they may rely on a third part for documents retention by a non-disclosure agreement to protect data confidentiality.

14.7 Clinical Study Report

The clinical study report shall be completed by the sponsor, or a designed delegate by the means of a non-disclosure agreement, even if the study will be terminated prematurely, only after:

- all queries concerning the eCRF will be closed;
- the database will be locked;
- the statistical report will be written and approved.

The sponsor will draft the clinical study report after the finalization of the statistical report. The clinical study report will be reviewed and approved by the investigator and, as soon as available, shall be provided to the relevant IEC and authorities (when applicable).

14.8 Insurance and Liability

No additional procedures for the patients nor for the investigational team members are planned for the present observational study with respect to the normal clinical practice, that actually comprises a retrospective and prospective data collection. The sponsor, therefore, is not requested to put in place an additional dedicated liability insurance covering this study.

14.9 Financial Disclosure

Assumed this is a sponsored study, after the relevant IEC and authority approval/authorization the sponsor will put in place with the hospital administration of the site an agreement that will allow to pay the involved department for study execution.

The information regarding Financial Disclosure of the Investigator will be collected and retained in the Trial Master File.

14.10 Publication

The sponsor and the investigator intend to compile a comprehensive publication of study results in a peer review journal, within 6 months from study completion or early termination, appropriately addressing contributions of co-authors.

Co-authors will be designated by the investigator (study staff at the hospital e.g. sub-investigator) and by the sponsor from the staff involved in the design and conduction of the study.

The sponsor recognizes the right and interest of co-authors, to scientifically publish the results obtained from the study for non-commercial purposes, even if the effects ascribed to the investigational product fail to materialize. All article or scientific presentation from investigator and co-authors can be published only after the first publication of the results by the sponsor.

The sponsor, together with the investigator, reserve the right to publish and present the results of this study at scientific congresses, to submit these clinical trial data to national and international Regulatory Authorities.

At least 30 days before any publication or presentation of study results, co-authors agree in submitting a manuscript/abstract of the intended publication or presentation to the sponsor for review. The sponsor will provide its revision within 15 working days. Proposals for changes and modifications raised by sponsor will be taken into consideration by the participating Investigators if such proposals do not interfere with the scientific nature and content of the publication.

The identity of the sponsor and the nature of his contribution to this study shall be disclosed in any publication or presentation.

The sponsor, according to current EU regulation (MDR 2017/45) and guidelines (ISO 14155) is responsible to register the study in a publicly accessible database. The current status and details of the study is publicly accessible on ClinicalTrials.gov at the registration nr. NCT05612139.

16. APPENDICES

16.1 Appendix 1: Investigational Device items catalog number

Sterile version:

CATALOG NUMBER	DESCRIPTION
99-67735100	JTIN TELESCOPIC NAIL L100MM D3.5MM STERILE
99-67735120	JTIN TELESCOPIC NAIL L120MM D3.5MM STERILE
99-67735130	JTIN TELESCOPIC NAIL L130MM D3.5MM STERILE
99-67735140	JTIN TELESCOPIC NAIL L140MM D3.5MM STERILE
99-67735150	JTIN TELESCOPIC NAIL L150MM D3.5MM STERILE
99-67740130	JTIN TELESCOPIC NAIL L130MM D4.0MM STERILE
99-67740155	JTIN TELESCOPIC NAIL L155MM D4.0MM STERILE
99-67740180	JTIN TELESCOPIC NAIL L180MM D4.0MM STERILE
99-67740205	JTIN TELESCOPIC NAIL L205MM D4.0MM STERILE
99-67740230	JTIN TELESCOPIC NAIL L230MM D4.0MM STERILE
99-67745160	JTIN TELESCOPIC NAIL L160MM D4.5MM STERILE
99-67745175	JTIN TELESCOPIC NAIL L175MM D4.5MM STERILE
99-67745190	JTIN TELESCOPIC NAIL L190MM D4.5MM STERILE
99-67745205	JTIN TELESCOPIC NAIL L205MM D4.5MM STERILE
99-67745230	JTIN TELESCOPIC NAIL L230MM D4.5MM STERILE
99-67750250	JTIN TELESCOPIC NAIL L250MM D5.0MM STERILE
99-67750275	JTIN TELESCOPIC NAIL L275MM D5.0MM STERILE
99-67750300	JTIN TELESCOPIC NAIL L300MM D5.0MM STERILE
99-67750325	JTIN TELESCOPIC NAIL L325MM D5.0MM STERILE
99-67750350	JTIN TELESCOPIC NAIL L350MM D5.0MM STERILE
99-67760250	JTIN TELESCOPIC NAIL L250MM D6.0MM STERILE
99-67760275	JTIN TELESCOPIC NAIL L275MM D6.0MM STERILE
99-67760300	JTIN TELESCOPIC NAIL L300MM D6.0MM STERILE
99-67760325	JTIN TELESCOPIC NAIL L325MM D6.0MM STERILE
99-67760350	JTIN TELESCOPIC NAIL L350MM D6.0MM STERILE

Non-sterile version

CATALOG NUMBER	DESCRIPTION
67735100	JTIN TELESCOPIC NAIL L100MM D3.5MM
67735120	JTIN TELESCOPIC NAIL L120MM D3.5MM
67735130	JTIN TELESCOPIC NAIL L130MM D3.5MM
67735140	JTIN TELESCOPIC NAIL L140MM D3.5MM
67735150	JTIN TELESCOPIC NAIL L150MM D3.5MM
67740130	JTIN TELESCOPIC NAIL L130MM D4.0MM
67740155	JTIN TELESCOPIC NAIL L155MM D4.0MM
67740180	JTIN TELESCOPIC NAIL L180MM D4.0MM
67740205	JTIN TELESCOPIC NAIL L205MM D4.0MM
67740230	JTIN TELESCOPIC NAIL L230MM D4.0MM
67745160	JTIN TELESCOPIC NAIL L160MM D4.5MM
67745175	JTIN TELESCOPIC NAIL L175MM D4.5MM
67745190	JTIN TELESCOPIC NAIL L190MM D4.5MM
67745205	JTIN TELESCOPIC NAIL L205MM D4.5MM

67745230	JTIN TELESCOPIC NAIL L230MM D4.5MM
67750250	JTIN TELESCOPIC NAIL L250MM D5.0MM
67750275	JTIN TELESCOPIC NAIL L275MM D5.0MM
67750300	JTIN TELESCOPIC NAIL L300MM D5.0MM
67750325	JTIN TELESCOPIC NAIL L325MM D5.0MM
67750350	JTIN TELESCOPIC NAIL L350MM D5.0MM
67760250	JTIN TELESCOPIC NAIL L250MM D6.0MM

1 GLOSSARY

Abbreviation	Explanation
ADE	Adverse Device Effect
AE	Adverse Event
ASADE	Anticipated serious adverse device effect
CE	Conformité Européenne (European Conformity)
CI	Confidence Interval
CRF	Case Report Form
CRO	Contract Research Organization
CV	Curriculum Vitae
FAS	Full Analysis Set
FAIS	The Full Analysis Implant Set
GCP	Good Clinical Practice
GP	General Practitioner
ICH	International Conference on Harmonization of Technical Requirements for Registration of Pharmaceuticals for Human Use
IEC	Independent Ethics Committee
JTIN	JuniOrtho™ Telescopic Intramedullary Nail
Max	Maximum
MDDs	Medical Device Deficiencies
MDR	Medical Device Regulation (EU 2017/745)
Min	Minimum
OT	Operative Technique
OI	Osteogenesis Imperfecta
Q	Quarter
PMCF	Post-Market Clinical Follow-up
IFU	Instruction for Use
ITT	Intention-To-Treat
PP	Per-Protocol
SAE	Serious Adverse Event
SAP	Statistical Analysis Plan
SD	Standard Deviation
SDV	Source Data Verification
TMF	Trial Master File
ROM	Range of Motion
SOA	State-of-art
USADE	Unanticipated serious adverse device effect
WBP	Weight Bearing Protocol

2 INTRODUCTION

A manufacturer of a medical device must demonstrate that the intended purpose(s) and claim(s) made in relation to safety and performance of a medical device are achieved. As a general rule, such demonstration will require clinical data. Clinical data are relevant to the various aspects of the clinical safety and performance of the device. This may include data from prospective and retrospective clinical investigations of the concerned device as well as market experience of the same or equivalent devices and medical procedures and information from the scientific literature. The aim of the present study is to collect post-market clinical evidence (post-market clinical follow up PMCF) on the use of the medical device JuniOrtho™ Telescopic Intramedullary Nail (JTIN).

2.1 BACKGROUND INFORMATION

Osteogenesis Imperfecta (OI), also called brittle bone disease, is a group of genetic disorders that affect connective tissue due to a lack of type I collagen. The classical Sillence types of OI (types I-IV) with autosomal dominant inheritance comprise about 80-85% of cases and are caused by mutations in the genes that encode type I collagen, COL1A1 and COL1A2.

Osteogenesis imperfecta is a very polymorphic condition, apart from the classical autosomal dominant forms, there are also recessive forms, often severe. Forms with hyperthrophic calluses (type V DA), and others associated with joint contractures (Bruck's syndrome).

Currently, more than twenty affections are identified clinically and by molecular biology studies. The incidence of forms recognizable at birth is 1:10-20,000. The hallmark feature of OI is bone fragility, with susceptibility to fracture from minimal trauma, as well as bone deformity and growth deficiency. Secondary features include dentinogenesis imperfecta (DI), cardiopulmonary complications and, in adult years, hearing loss. The clinical features of OI represent a continuum ranging from perinatal lethality to individuals with severe skeletal deformities, mobility impairments, and very short stature to nearly asymptomatic individuals with a mild predisposition to fractures, normal dentition, normal stature, and normal life span.

Fractures can occur in any bone but are most common in the limbs.

Management is ideally done by a multidisciplinary team including specialists in medical management of OI, clinical genetics, orthopedics, endocrinologist, rehabilitation medicine, paediatric dentistry, otology/otolaryngology, and mental health.

Intramedullary nails have an important role for bone stabilization and fracture prevention in patients with OI, who suffer from bone fragility and recurrent fractures. Long bones in the lower limbs of OI patients are especially prone to deformities that develop as a result of bone deformability or from malunion in fractures. Thus, it is important to provide structural support to

the weakened bones of these patients, which is better accomplished with the use of intramedullary devices.

The objectives of long bone rodding in OI patients are to:

- Fracture treatment;
- Correct deformity;
- Improve function;
- Restore bone density through functional load bearing.

2.2 RATIONALE OF THE STUDY

Orthofix Srl put the JTIN on the European market (2021) by the mean of a pre-market clinical evaluation made under the Medical Device Directive (MDD) requirements that was based on the analysis of the scientific literature of equivalent devices.

This study has been planned as part of the Orthofix Srl post-market active surveillance plan for the collection of data on both the clinical performance and the safety profile of the JTIN in a representative population of patients and users.

The rationale of the proposed study is to update and support the pre-market clinical evaluation of the JTIN with real-word-evidence clinical data, in order to confirm the benefit/risk ratio of this medical device and to keep the CE mark under Medical Device Regulation (MDR) requirements. The uniqueness of the pediatric population manifests itself in specific indications for lower extremity reconstruction, due to osteogenesis imperfecta; different approach in compliance with operative and postoperative care in addition to need for adaptability to rapid growth and development. The JuniOrtho™ Telescopic Intramedullary Nail (JTIN) is an established, marketed device, commercially available and used as standard device in orthopedic surgeries.

The post-marketing, prospective study with CE-marked device JuniOrtho™ Telescopic Intramedullary Nail (JTIN) is designed for gathering real-world medical data from treatment of fractures, osteotomies/ bone deformities, malunions and non-unions in femur and tibia in pediatric patients (older than 18 months) suffering from osteogenesis imperfecta.

All data will be gathered from standard medical documentation from patients who have already been successfully treated with JTIN. Additionally, all procedures that patients underwent are justified by standard of care.

Constant identification of serious or unexpected serious risk related to the use of the device, especially in real-world experience may bring additional data, that can contribute to the safety of future patients.

In conclusion, patients will not directly benefit from the participation in this study but no additional risk related to the study participation is to be recognized.

3 PROTOCOL AND CRF VERSION

Protocol version: MARTOM_OCI_2201_JTIN_V1.1_02082024 - signed

CRF version: JTIN_OCI_2201_Visits_eCRF vs.28.71_20Nov2024 and
JTIN_OCI_2201_AE_MDD_eCRF vs 28.71_20Nov2024

4 OBJECTIVES OF THE ANALYSIS PLAN

The analysis plan proposed below describes the aspects needed to know about the study and the statistical analysis methods to be used to apply them to the data collected and respond to the study objectives.

5 PRIMARY STUDY OBJECTIVE

The primary objective of the study is to evaluate the clinical safety profile of JTIN within the scope of its intended purpose, when used according to the manufacturer IFU on a representative population of subjects and users.

6 SECONDARY STUDY OBJECTIVES

The secondary objective of the study is to evaluate the clinical safety and performance of JTIN by the three following endpoints, when the MD is used within the scope and according to the manufacturer IFU.

7 EXPLORATORY OBJECTIVE

The Gillette Functional Assessment Questionnaire will be collected, according to hospital standard care, before the surgery Visit 0 (screening)) and at 1 year follow up (Visit 6), to evaluate the changes after treatment.

[figure not shown]
The questionnaire is performed by the investigator the first time (i.e. before the surgery) observing the patient (in presence or eventually via telemedicine), and for the follow-up it can be performed by the investigator by telephone or by email with the parent (or legal representative). The Gillette Functional Assessment Questionnaire is not specific developed for OI patients but it is used in the hospital because no other score is currently available specifically for OI patients. The hospital is aware that other factors for OI patient can interfere with the score.

8 STUDY DESIGN

This is a Post Market Clinical Follow-up (PMCF) study which is prospective and retrospective, observational, single-center, not controlled.

No requirements regarding the treatment of patients will be imposed on the Site or Principal Investigator and the Sponsor will not in any manner influence the treatment decisions of Principal Investigator (i.e. non-interventional). The enrolment of patients and their treatment, including diagnostics and monitoring, will be guided solely by the principles of normal medical practice and the Principal Investigator's sole medical judgment. Site and Principal Investigator will ensure that the Device is used in accordance with normal medical practice and the instructions for use. The subjects will not undergo additional visit nor non-invasive, invasive or burdensome procedures additional to those performed under the normal clinical practice.

Figure 1. Study schematic diagram

9 STUDY POPULATION

This study will be conducted only on patients with a regular indication for JTIN as per IFU (no off-label use will be included): the nail is indicated for fractures, osteotomies, malunions and non-unions in femur and tibia in pediatric patients suffering from osteogenesis imperfecta. The JTIN is intended to be used in pediatric patients, older than 18 months.

This study includes only one site (monocentric) located in Paris, France. The site was chosen for this study due to the number of subject devices already implanted, and the wideness of the indications covered by the surgeries. The site was also positively evaluated by sponsor for the appropriate qualification and competency of the investigator and of the staff, and availability of facilities and equipment.

Sample size calculation:

Due to the observational nature of the study, no formal sample size calculation has been done, but a revision of the literature on the complication rates (intended as at least one serious/not serious adverse event certainly or possibly related to the procedure up to 1 year follow-up) has been made. The scientific literature reports that the percentage of procedures which develop at least one serious/not serious adverse event certainly or possibly related to the procedure itself is between 9% and 60%, with a mean of 31%. Assuming a complication rate aligned or better than the mean observed in literature (31%), a sample size of 15 procedures will be sufficient to estimate the adverse event rate with the upper limit of the 95% confidence interval equal or lower than the worst complication rate seen in literature (i.e. 60%).

Starting from this sample size, to also assume that the success rate (intended as proportion of procedures that result in a bone union achieved) is aligned or better than the mean observed in literature (80%), 20 procedures will be needed.

Considering a drop-out or a non-evaluable rate of 20% of the procedures, a total of approximately 25 procedures should be made. Each subject could have from 1 to 4 procedures. Assuming the worst scenario of no more than 1 procedure for subjects, a maximum of 25 subjects needs to be enrolled. Anyway, the enrolment will stop when the total number of the procedures is reached.

10 STUDY DURATION

The study duration at the site is planned for 1,5 years (18 months), that includes the enrolment period of 6 months plus 1 year of data collection up to last patient last visit.

The study duration for each subject implant is approximately 1 year from the date of surgery, according to the visit schedule. Since the subjects will follow standard clinical care of the site and due to the observational character of the study, the study duration for each subject can be slightly different according to the standard of care.

11 INCLUSION CRITERIA

A patient will be included in the study if:

- is in pediatric age (> 18 month and < 18 years) at the time of surgery;
- is skeletally immature;
- has a diagnosis for OI;
- has a regular indication for surgical intervention with JTIN to treat femoral and/or tibial fractures, osteotomies, malunions and non-unions;
- Patient and/or legal representative is duly informed and doesn't oppose to participation.

12 EXCLUSION CRITERIA

A patient will not be included in the study who:

- has a medical condition that is a contraindication according to the manufacturer's instruction for use;
- has any conditions that in the Investigator's opinion may interfere with the study execution or due to which the patient should not participate for safety reasons;
- requires the application of, or has already in-situ the application of concomitant devices that cannot be safely removed (except for permitted concomitant devices paragraph);
- is participating in other clinical trials or has taken part in any clinical study in the last 3 months with exception of analytical trials on genetics study related to OI (i.e. studies that do not include an investigational treatment for the patient such as new drugs or other medical devices);
- is likely to be lost to follow up, according to investigator's opinion.

13 ANALYSIS POPULATION

- **The Full Analysis Set (FAS) population** will consist of all enrolled patients treated by the means of JTIN application and who didn't oppose to study participation. The FAS population will be used for all the analyses of the study that are presented at subject level.
- **The Full Analysis Implant Set (FAIS) population** will consist of all JTIN applications performed on subjects belonging to the FAS population. The FAIS population will be used for all the analyses of the study that are presented at implant level.

The CRF contains the selection criteria information in the form of a binary variable (Yes/No) for each element described. Patients are considered to belong to the FAS and FAIS populations if they indicate that they meet the selection criteria in the previously mentioned binary variables.

Several of these criteria can be verified with the data recorded in the CRF. The criteria to be verified to define the FAS and FAIS population for the analysis are described below:

INCLUSION CRITERIA

1. *is in pediatric age (> 18 month and < 18 years) at the time of surgery;* The patients' age at surgery must be between 18 months and 18 years.
2. *is skeletally immature;* This criteria cannot be verified with the variables included in the CRF.
3. *has a diagnosis for OI;* The variables "OI Type Diagnosis" and "Treated bone" should be collected in screening visit.
4. *has a regular indication for surgical intervention with JTIN to treat femoral and/or tibial fractures, osteotomies, malunions and non-unions;* The variable "Intended use of JTIN for this case" should be collected in screening visit.
5. *Patient and/or legal representative is duly informed and doesn't oppose to participation.*
This criteria cannot be verified with the variables included in the CRF.

EXCLUSION CRITERIA

1. *has a medical condition that is a contraindication according to the manufacturer's instruction for use;* This criteria cannot be verified with the variables included in the CRF.
2. *has any conditions that in the Investigator's opinion may interfere with the study execution or due to which the patient should not participate for safety reasons;* This criteria cannot be verified with the variables included in the CRF.
3. *requires the application of, or has already in-situ the application of concomitant devices that cannot be safely removed (except for permitted concomitant devices paragraph);* This criteria cannot be verified with the variables included in the CRF.

4. *is participating in other clinical trials or has taken part in any clinical study in the last 3 months with exception of analytical trials on genetics study related to OI (i.e. studies that do not include an investigational treatment for the patient such as new drugs or other medical devices);* This criteria cannot be verified with the variables included in the CRF.
5. *is likely to be lost to follow up, according to investigator's opinion.* This criteria cannot be verified with the variables included in the CRF.

A list of patients belonging to each of the populations will be sent to the sponsor for confirmation prior to analysis.

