8.3 Subject Withdrawal

Premature discontinuation from the study will occur when an enrolled patient (namely a patient who doesn't oppose to participation) will not undergo the final follow-up visit.

At any time patients may prematurely discontinue from this study for any reason, without explanation and without losing the right to future medical care. The participation of the patient may, at any moment, be terminated by the Investigator as well, if considered appropriate (i.e. the early termination is in the patient's best medical interest).

Patients who prematurely terminate the study are considered as "withdrawal" ("drop out") patients. Possible reasons for withdrawal of a patient from the study are:

- lack of adequate therapeutic response resulting in an unacceptable risk;
- major protocol violation;
- an inclusion or exclusion criteria that becomes invalid;
- serious or intolerable AE preventing the patient from continuing the study;

- refusal of the patient to continue the treatment and/or protocol procedures;
- decision by the Investigator if it would not be in the best interest of the patient to continue the study;
- lost to follow-up;
- death of the patient.

It is understood by all concerned that an excessive rate of withdrawals can render the study not interpretable, therefore, withdrawals of patients should be carefully assessed. However, if a patient decides to withdraw for any reason, all efforts will be made to complete and report the observations as thoroughly as possible in the patient's records and with an end-of-study visit page that will be available in the electronic Case Report Form (eCRF).

Any subject withdrawal, including lost to follow-up, must be traced by the investigator in the patient medical file and in the eCRF, including the possible reasons.

Until such time that the enrolment period is officially closed by the Sponsor, any withdrawn patients may be replaced by recruitment in accordance with the aforementioned protocol to reach the planned number of evaluable cases. The screening number assigned to the withdrawn patient will not be reassigned to another patient.

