12.1.1 Population(s) of analysis

The following populations will be defined:

- The Full Analysis Set (FAS) population will consist of all enrolled patients treated by the means of JTIN application and who didn't oppose to study participation. The FAS population will be used for all the analyses of the study that are presented at subject level.
- The Full Analysis Implant Set (FAIS) population will consist of all JTIN applications performed on subjects belonging to the FAS population. The FAIS population will be used for all the analyses of the study that are presented at implant level.

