22 STUDY EXIT VISIT

This analysis will be performed on FAIS population.

The categorical variables to be described are, N and (%):

- Reason for study exit
 - Subject completed protocol last visit
 - Nail removed
 - Subject does not meet inclusion criteria (a list will be shown)
 - Subject withdrew consent
 - Subject withdrawn by Investigator (a list will be shown)
 - Subject Death
 - Lost to follow-up
 - Subject had an AE that does not permit the continuation of the study (specify nr. of AE: a list will be shown)
 - Other Reason (a list will be shown)

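### SAP 13 adds an eligibility condition to FAS/FAIS that the protocol does not contain, which could exclude an implanted case enrolled in error from the primary safety analysis

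*SAP*

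**What the plan says.** Protocol 12.1.1 states that the FAS "will consist of all enrolled patients treated by the means of JTIN application and who didn't oppose to study participation". For the FAIS, it states that the "population will consist of all JTIN applications performed on subjects belonging to the FAS population". Neither definition mentions the selection criteria. Protocol 8.3 shows what *enrolled* means in this study: it speaks of "an enrolled patient (namely a patient who doesn't oppose to participation", so the term rests on non-opposition.

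SAP 13 restates both definitions. It then says that the CRF holds a yes/no variable for each criterion and adds: "Patients are considered to belong to the FAS and FAIS populations if they indicate that they meet the selection criteria" in those variables. It goes on to list criteria that are to be checked against CRF data in order to define the two sets. Age at surgery must be in range; OI type, treated bone and intended use should have been recorded at screening. The other seven of the ten criteria (inclusion 2 and 5, exclusion 1 to 5) are described as not verifiable from the CRF. The section ends: "A list of patients belonging to each of the populations will be sent to the sponsor for confirmation prior to analysis".

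SAP 23 runs the primary safety analysis on FAS/FAIS. Neither document defines a separate safety set of all implanted cases.

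**The concern.** Two rules govern the same analysis set, and only one of them is in the protocol. For a patient who was implanted, did not oppose, and was later found to fail a criterion, the protocol rule keeps the case and the added SAP rule points to leaving it out. Since FAS/FAIS is the only set used for the primary endpoint, the case would take its adverse events with it.

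The primary endpoint is the percentage of procedures with a certainly or possibly device-related adverse event within one year. With 20 to 25 procedures planned, one or two cases move that percentage visibly. Membership would be settled from collected CRF data shortly before analysis, in an open-label single-arm study, when events may already be on record. The safeguard is a membership rule that leaves no room for choice, and the SAP at present has two.

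**Working it through.** **1. The two rules side by side**

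- Protocol 12.1.1: enrolled, treated with JTIN, did not oppose.
- SAP 13, restated definition: the same.
- SAP 13, added rule: selection-criteria variables answered as met, with age and screening variables checked to define the sets.

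The added sentence says *if*, not *only if*. But a check carried out to define a set has no purpose unless it can affect membership, so the natural reading is a filter.

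**2. Who is treated differently**

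Protocol 10.2.1 says patients who fail the criteria must not be enrolled. The rules therefore diverge only for a patient enrolled in error. The documents do not say how many to expect.

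**3. The plan's own figures**

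Inputs from Protocol 12.3: assumed rate 31%, benchmark upper limit 60%, 20 evaluable procedures, 20% non-evaluable. SAP 14 names Clopper-Pearson 95% intervals:

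- lower limit = Beta quantile 0.025 with parameters (x, n − x + 1)
- upper limit = Beta quantile 0.975 with parameters (x + 1, n − x)

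With x = 0.31n (a fractional count), the upper limit is 60.5% at n = 14 and 59.4% at n = 15, so the stated 15 is reproduced. 20 / (1 − 0.20) = 25 is also reproduced. No planned number is wrong, and the fix changes none of them.

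**4. Sensitivity of the primary percentage to membership**

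The event counts are set near the plan's 31%: 0.31 × 25 = 7.75, taken as 8; 0.31 × 20 = 6.2, taken as 6. The number removed (one to three) is an assumption.

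| Removed | From 8/25 | From 6/20 |
|---|---|---|
| None | 32.0% (14.9 to 53.5) | 30.0% (11.9 to 54.3) |
| 1 event case | 7/24 = 29.2% (12.6 to 51.1) | 5/19 = 26.3% (9.1 to 51.2) |
| 2 event cases | 6/23 = 26.1% (10.2 to 48.4) | 4/18 = 22.2% (6.4 to 47.6) |
| 3 event cases | 5/22 = 22.7% (7.8 to 45.4) | 3/17 = 17.6% (3.8 to 43.4) |
| 1 event-free case | 8/24 = 33.3% (15.6 to 55.3) | 6/19 = 31.6% (12.6 to 56.6) |
| 2 event-free cases | 8/23 = 34.8% (16.4 to 57.3) | 6/18 = 33.3% (13.3 to 59.0) |
| 3 event-free cases | 8/22 = 36.4% (17.2 to 59.3) | 6/17 = 35.3% (14.2 to 61.7) |

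From 8/25, removing two event cases lowers the estimate by 32.0 − 26.1 = 5.9 points. Removing two event-free cases raises it by 34.8 − 32.0 = 2.8 points.

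**The case against.** The strongest reply is that the gap is narrow. Only patients who meet all criteria are approached and given an eCRF record (Protocol 7.4.2), those who fail must not be enrolled (10.2.1), and the criteria receive 100% source verification (14.2). On that view SAP 13 merely puts *enrolled* into operation. The reply limits how often the rules can differ. It does not reconcile them, because the protocol's own gloss on *enrolled* is non-opposition.

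A second reply is that the study excludes off-label use (Protocol 7.2) and aims at use according to the IFU (6.1), so an eligibility filter serves the objective. That is a fair reason to report an IFU-conforming set. It does not place the condition in Protocol 12.1.1.

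Several stronger readings are tempting, but the documents do not support them:

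- **The exit code proves the filter.** SAP 22 lists "Subject does not meet inclusion criteria (a list will be shown") as an exit reason, but that table is itself run on the FAIS, so such cases are counted inside the set.
- **A criterion that lapses later removes the case.** Protocol 8.3 lists "an inclusion or exclusion criteria that becomes invalid" as a reason for withdrawal. Withdrawal ends follow-up; neither document says that it ends set membership.
- **A blank OI type removes the case.** SAP 13 says the field should be collected and states no consequence if it is not.
- **The table of reasons for non-membership (SAP 15.1) proves the filter.** That table is needed in any event for enrolled patients who never receive a nail.
- **The sponsor may choose who counts.** SAP 13 asks for confirmation of a list and grants no power to change it. What is missing is a stated limit.

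The illustration also has its limits. The shifts go both ways, the two-case examples stay below the 60% benchmark, and no hypothesis test of the primary endpoint depends on them.

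**Conclusion.** The concern holds in a limited form. SAP 13 carries the protocol's definition and a narrower one together, and following the narrower one could exclude an implanted case enrolled in error, with its adverse events, from the only set used for the primary safety endpoint. It cannot be said that the SAP will remove cases: the number affected is unknown and may be zero. If it is not zero, two exclusions from an assumed 8/25 would place the estimate anywhere from 26.1% to 34.8%, depending on whether the excluded cases had events. This rests on reading the added sentence as a condition for membership and on event counts close to the plan's 31%. It should be corrected before analysis, as a matter of SAP consistency that also closes a possible route to bias.

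**What to change.** In SAP 13, delete the sentence that ties membership to the selection-criteria variables and the statement that the checked criteria define the sets. Use the Protocol 12.1.1 wording, including *enrolled*, as the sole FAS/FAIS rule for the primary safety analysis.

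Keep the CRF checks for two other purposes: a listing of eligibility deviations (Protocol 14.5 already requires deviations to be reported) and a named criteria-verified, IFU-conforming set, with the primary endpoint repeated on it as a sensitivity analysis. That meets the no-off-label rule and the IFU-based objective without narrowing the main set. Add one sentence saying that the sponsor's confirmation of the population list covers completeness only.

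The cost is a few lines of SAP text and one sensitivity table, which can be omitted if no case fails a criterion. Data collection and the planned 20 evaluable and 25 total procedures are unchanged.
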